5.2 Planned subgroup analyses

- (i) Size of tear (small versus medium/large);
- (ii) Age <65 or ≥65;

Stricter levels of statistical significance ($2p < 0.01$) will be sought, reflecting the exploratory nature of these subgroup analyses.

5.3 Statistical analysis

Reflecting the possible clustering in the data, the outcomes will be compared using multilevel models, with adjustment for minimisation variables and participant baseline values. Statistical significance will be at the 2.5% level with corresponding confidence intervals will be derived. All participants will remain in their allocated group for analysis (intention to treat). Comparisons (i) and (ii) will be based upon the respective direct randomised evidence only. For comparison (iii), a meta analysis will be used to combine the results from the direct comparison (using stratum A) and an indirect comparison (using strata B and C). A secondary analysis will investigate the impact of surgical expertise level (learning curve effects)¹⁷. All study analyses will be according to a statistical analysis plan that will be agreed in advance by the Trial Steering Committee. A single main analysis will be performed at the end of the trial when all follow up has been completed. An independent Data Monitoring Committee (DMC) will meet early in the trial to agree its terms of reference and other procedures and will review confidential interim analyses of accumulating data at least annually as directed.

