[name], Senior Lecturer in Medical Statistics, London

UKUFF Study Team in Oxford

[name], [name], [name], [name], [name], [name], [name] and [name]

UKUFF Study Team in Aberdeen

[name], [name], [name], [name], [name], [name], [name] and [name]

Other Information

International Standard Randomised
Controlled Trial Number (ISRCTN) ISRCTN97804283
REC Reference Number 07/Q1606/49
REC Version Number Version 1, April 2008
HTA Project Number 05/47/02

The clinical and cost-effectiveness of surgical (arthroscopic or open) versus Rest then Exercise management for tears of the rotator cuff

This protocol describes a major multi-centre UK trial to assess the clinical and cost effectiveness of arthroscopic surgery, open surgery and a Rest then Exercise program in the management of rotator cuff tears. For the surgical arms the surgeons will undertake their usual and preferred surgical techniques while the conservative management arm will comprise of a month of rest and then up to 12 weeks of specialised shoulder exercises. This conservative programme has been designed specifically for the trial with the help of consumers, physiotherapists and shoulder surgeons.

The eligibility of the patient will be assessed by the local consultant orthopaedic surgeon, with consent being obtained either locally by a research nurse or remotely by the study office in Oxford. Only when the consent form and the baseline questionnaire are returned will the participant enter the trial and be randomised to one of the three management arms. The patients will continue to be followed up at 2 and 8 weeks post treatment and 8, 12, and 24 months post randomisation.

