2.2 Design

A detailed survey of 126 surgeons from the British Elbow & Shoulder Society (BESS), carried out in preparation for this study, showed that the majority of surgeons practice only open surgery for rotator cuff repairs. A number of surgeons did indicate a willingness to randomise between arthroscopic and open surgery although the majority showed no equipoise for the two different techniques. Reflecting this lack of individual uncertainty around certain comparisons, randomisation will be organised within three strata depending on the surgeons' preparedness to randomise. The three strata are:

StratumA	arthroscopic surgery versus open surgery versus Rest then Exercise
StratumB	arthroscopic surgery versus Rest then Exercise
StratumC	open surgery versus Rest then Exercise

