3.4 Randomisation procedures

When the full consent form and the baseline questionnaire have been received by the study office in Oxford the participant will be randomised to one of the management programmes. Randomisation will be by computer allocation using the service provided by the Health Services Research Unit, University of Aberdeen. Allocation will be stratified by the surgical technique performed by the surgeon (open and/or arthroscopic) and minimised using centre, age and size of tear. After randomisation the participant is considered irrevocably part of the trial for the purpose of the research, irrespective of what occurs subsequently.

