3.4.2 Randomisation to conservative arm

The study office in Oxford will send an allocation letter to the participant along with an information pack containing a self-help CD, self-help booklet and a sling (Appendix II). The participants will be asked if they have access to a DVD player or computer, although the information contained on the CD is identical to the information in the booklet. To ensure the participants receive the information pack, a reply slip will be enclosed with the pack asking the participants to check the contents and then return the slip to the study office in Oxford. The consultant surgeon and the participants GP will also receive letters outlining that their patient has been randomised to the conservative management programme (Appendix II). All participants randomised to the conservative arm will receive the same information and advice. If they require further information about non-surgical care they will have access to a

telephone free-call help-line where clinical staff and/or the research physiotherapist will be available to answer questions and provide advice. The patients GPs will also be asked to inform the study office if the patient consults them regarding any physiotherapy treatments. This information is important as attending a physiotherapy session may alter the outcomes of the programme and so all sessions need to be documented.

The Rest then Exercise participants will be placed on the NHS waiting list for surgery at the same time as the surgical arm participants. Due to the length of most of the Trust's NHS waiting lists, they should be able to complete the Rest then Exercise programme before they would be due for surgery. However, it is anticipated that a few participants may have their date of surgery delayed while they complete the programme, although this is not anticipated to be a regular occurrence. Surgeons are asked to contact the study office if their patients decline surgery after the completion of the Rest then Exercise Programme.

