6. SAMPLE SIZE AND FEASIBILITY

6.1 Sample size sought

Based on our experience of using and developing the OSS score in a variety of settings, a 3 point difference (0.33 of a SD) would be deemed a clinically important change. Using the informal survey of surgeons' preferences, we aim to recruit at least 8 surgeons to stratum A, 10 to stratum B and 40 to stratum C. From this we have assumed the following numbers of participants in each strata: Stratum A – 70 participants in each group; stratum B - 120 arthroscopic surgery : 120 Rest then Exercise management and stratum C - 120 open surgery : 120 Rest then Exercise management (see Table 1) giving 690 participants in total.

Table 1 – Proposed number of randomised participants

	Arthroscopic surgery	Open surgery	Rest then Exercise
Stratum A	70	70	70
Stratum B	120	None	120
Stratum C	None	120	120

For comparison (i), results from the arthroscopic surgery and Rest then Exercise groups in strata A and B can be combined without introducing any systematic bias (resulting in 190 arthroscopic:190 Rest then Exercise). Such a study has greater than 80% power at 2.5% significance level (to account for multiple testing) to detect a difference in mean OSS of 0.33 of a SD, using a two sample two-sided t-test. With an SD of about 9, this would translate to having adequate power to be able to detect a difference in mean OSS score between two groups of about 3 units.

For comparison (ii), the same power (>80%) and detectable difference (0.33 of a SD) as given above are obtained by combining the open surgery and Rest then Exercise management groups in strata A and C (n=190 in each arm).

[figure not shown]
For comparison (iii), due to the small numbers of surgeons willing to randomise to this comparison we propose to use a mixture of direct (randomised) and indirect (non randomised) comparisons. The direct comparison is in stratum A where 70 arthroscopic: 70 open surgeries have 80% power at 2.5% significance to detect a difference of 0.5 of a SD. An indirect comparison using only the results from strata B and C would have 80% power (at 2.5% significance level) to detect a difference of 0.55SD. Combining the direct and indirect comparison estimate (using recognised meta analysis techniques) gives approximately 80% power at 2.5% significance to detect a difference of 0.38SD.

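### The indirect half of open versus arthroscopic assumes that Rest then Exercise is the same comparator in strata B and C; later surgery may make it differ, and the 0.38 SD power statement makes no allowance for this

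*Protocol*

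**What the plan says.** Protocol section 5 makes open versus arthroscopic surgery a principal comparison, (iii). Section 5.3 will "combine the results from the direct comparison (using stratum A) and an indirect comparison (using strata B and C"), with every participant analysed as allocated. Section 6.1 gives the resulting precision: "Combining the direct and indirect comparison estimate (using recognised meta analysis techniques) gives approximately 80% power at 2.5% significance to detect a difference of 0.38SD".

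On strata, section 2.2 says "randomisation will be organised within three strata depending on" what each surgeon is willing to randomise. Stratum B is arthroscopic against Rest then Exercise; stratum C is open against Rest then Exercise. Section 3.4 ties the strata to practice: "Allocation will be stratified by the surgical technique performed by the surgeon (open and/or arthroscopic"). Section 2.2 also reports that "the majority of surgeons practice only open surgery for rotator cuff repairs".

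On the comparator, section 3.4.2 says: "The Rest then Exercise participants will be placed on the NHS waiting list for surgery at the same time as the surgical arm participants". It adds: "Surgeons are asked to contact the study office if their patients decline surgery after the completion of the Rest then Exercise Programme". The opening description of the trial, ahead of section 1, gives the programme's length as "a month of rest and then up to 12 weeks of specialised shoulder exercises", about four months. The primary outcome (5.1) is the Oxford Shoulder Score at 24 months after randomisation.

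**The concern.** The indirect estimate is (arthroscopic − Rest then Exercise, in B) minus (open − Rest then Exercise, in C). The two Rest then Exercise terms cancel only if that arm has the same expected 24-month outcome in both strata.

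The protocol's own arrangements put this in doubt. The arm is listed for surgery from the start, it is those who decline whom surgeons must report, and about 20 months remain between the end of the programme and the primary endpoint. If later surgery follows the surgeon's technique, the reference arm becomes partly arthroscopic in B and partly open in C. The indirect estimate then no longer targets the arthroscopic-minus-open difference, yet it is averaged with a stratum A estimate that does not use this arm.

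This is distinct from dilution of comparisons (i) and (ii), which can be defended as a comparison of policies that include later surgery. In (iii) neither policy being compared contains Rest then Exercise. At stake are the size of the pooled estimate, the coverage of its interval, and the stated power for a principal comparison.

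**Working it through.** **Inputs.** From 6.1: 70 per arm in stratum A; 120 per arm in B and in C; 2.5% significance, taken as two-sided as for comparison (i); 80% power. Outcome in SD units. Surgery uptake p in Rest then Exercise by 24 months is not given, so it is varied.

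**Step 1: reproduce the protocol's figure.** Normal approximation, multiplier 2.241 + 0.842 = 3.083.
- Direct: variance 2/70 = 0.0286; detectable 3.083 × √0.0286 = 0.521 SD (stated 0.5).
- Indirect through Rest then Exercise, four groups of 120: variance 4/120 = 0.0333; detectable 0.563 SD (stated 0.55).
- Pooled by inverse variance: 1/(35 + 30) = 1/65, SE 0.124; detectable 0.382 SD (stated 0.38). Power at 0.38 SD: Φ(0.38/0.124 − 2.241) = 79%.

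A plain 120 v 120 contrast of arthroscopic in B with open in C would give 0.398 SD alone and 0.316 SD pooled, matching neither stated figure. The protocol's numbers therefore confirm that Rest then Exercise is the common comparator. Weights are 35/65 = 0.54 direct and 30/65 = 0.46 indirect.

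**Step 2: effect of later surgery, equal uptake.** Let A, O and R be the mean outcomes under arthroscopic surgery, open surgery and Rest then Exercise without later surgery. Suppose a share p has its stratum's technique and gains a fraction c of that technique's effect by 24 months. The reference arm is then R + pc(A − R) in B and R + pc(O − R) in C, so

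E[indirect] = (1 − pc)(A − O), and E[pooled] = (1 − 0.46pc)(A − O).

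For a true difference of 0.38 SD, power = Φ(0.38 × (1 − 0.4615pc)/0.124 − 2.241):

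| p (assumed) | c | Share of difference kept | Expected pooled (SD) | Power |
|---|---|---|---|---|
| 0 | – | 100% | 0.38 | 79% |
| 20% | 1 | 91% | 0.34 | 71% |
| 20% | 0.5 | 95% | 0.36 | 75% |
| 50% | 1 | 77% | 0.29 | 55% |
| 50% | 0.5 | 88% | 0.34 | 68% |
| 75% | 1 | 65% | 0.25 | 41% |
| 75% | 0.5 | 83% | 0.31 | 61% |

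**Step 3: unequal uptake, full catch-up.** E[indirect] = (1 − pB)(A − R) − (1 − pC)(O − R). If A = O this is (pC − pB) × the surgical effect, which can take either sign. With an assumed surgical effect of 0.33 SD, pB = 40% and pC = 60%, the indirect estimate is shifted by 0.2 × 0.33 = 0.066 SD and the pooled one by 0.46 × 0.066 = 0.03 SD, with no true difference. With a true 0.38 SD and the same average surgical effect, the expected pooled value is 0.32 SD at (40%, 60%) and 0.26 SD at (60%, 40%), against 0.29 SD at equal 50%. At mean uptake 50%, uptake would have to differ by 0.5 × 0.38/0.33 = 0.58, or 58 points, to cancel the dilution.

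**Step 4: pooled against stratum A alone.** Stratum A alone has Φ(0.38/0.169 − 2.241) = 50% power at 0.38 SD. With c = 1, pooling loses its power advantage when 1 − 0.4615p = √(35/65) = 0.734, that is p ≈ 0.58.

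**The case against.** The strongest reply has five parts.

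- **Technique is inferred.** Section 2.2 defines strata by willingness to randomise, and a stratum B surgeon need not operate only arthroscopically. No section states which operation a Rest then Exercise participant would later have. This stands as a qualification. Section 3.4, and the report in 2.2 that most surgeons do only open repair, make the inference the ordinary reading but not a stated fact.
- **Direction.** A reader might infer that the pooled estimate must be pulled towards no difference. That needs similar uptake in B and C, which the protocol does not give. Shrinkage is the expected net result, not a certainty.
- **Size.** Uptake is not given and full catch-up is the extreme case. This stands, and is why a range is shown.
- **Stratum A as the clean benchmark.** A reader might infer that the direct estimate is free of dilution and should replace the pooled one. Section 3.4.1 allows an alternative procedure when the allocated technique cannot be done, analysed as allocated, so stratum A can be diluted too. On power, pooling remains ahead up to p of about 0.58. Choosing between the two without knowing p is a trade-off.
- **Matter for the SAP.** Section 5.3 defers detail to an analysis plan, and consistency checks commonly sit there. Section 6.1 also openly calls the indirect part non-randomised and gives the direct, indirect and combined power separately. However, the protocol itself fixes the pooled estimator and states its power without this condition. Calling the indirect part non-randomised does not cover a comparator that changes after randomisation, and the allowances in 6.1 are for attrition and clustering only.

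**Conclusion.** The concern holds in a limited form. Comparison (iii) rests, for 46% of its weight, on a common comparator that the protocol's arrangements for later surgery may make different in B and C. The 0.38 SD power statement does not mention this. With similar uptake and full catch-up, the pooled estimate keeps about 1 − 0.46p of the true difference, and power at 0.38 SD falls from about 79% to 71%, 55% and 41% at p = 20%, 50% and 75%. At half catch-up the figures are 75%, 68% and 61%. With unequal uptake the error can go either way.

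This rests on assumed uptake, on later surgery following the stratum's technique, and on inverse-variance weights that reproduce the protocol's 0.38 SD. One further reading should be resisted: that the power figure is true only if no Rest then Exercise participant has surgery. The stated power is approximate, low uptake moves it little, and what it needs is that later surgery does not affect the 24-month contrast.

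**What to change.** **Section 6.1.** State that 80% power at 0.38 SD assumes later surgery in Rest then Exercise does not affect the 24-month contrast. Give the power for (iii) over a range of uptake and catch-up, as in the table above.

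**Section 5.3.** Keep the pooled estimate. Require the direct and indirect estimates to be reported separately beside it, with a direct-versus-indirect consistency check. Add a sensitivity analysis that adjusts the B and C contrasts for crossover before differencing, and state its assumptions. It will be imprecise: at p = 50%, dividing by (1 − p) multiplies the indirect variance by four, so its weight falls to 7.5/(35 + 7.5) = 18%.

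**Data collection.** State that the date and technique of any later surgery in Rest then Exercise participants are recorded and tabulated by stratum. Much of this exists already: 3.4.1 records operative details, 5.4 collects per-case theatre information, and 7.2.1 has surgeons report operation dates.

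**Cost.** Some protocol wording, a little more analysis and a less favourable power statement. Randomisation and care do not change.

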5.4 Economic evaluation

A cost-effectiveness analysis will be performed. A simple patient cost-related questionnaire will be sent out at baseline and at 12 and 24 months post randomisation, to obtain information on primary care consultations, other consultations, out-of-pocket costs, work-impact of the intervention received and return to work. Unit costs will come from national sources and participating hospitals. The patient questionnaire will also be used to administer the EQ-5D, which will also be obtained at baseline. The main health economic outcome will be within-trial and extrapolated quality adjusted life-years, estimated using the EQ-5D.

Incremental cost-effectiveness will be calculated as the net cost per quality-adjusted life year gained, for arthroscopic surgery versus Rest then Exercise, open surgery versus Rest then Exercise, either surgical versus Rest then Exercise and arthroscopic surgery versus open surgery. Power calculations (see following section) are based on clinical rather than cost-effectiveness outcomes, which will be estimated rather than used in hypothesis testing. Cost-effectiveness ratios and net-benefit statistics will be calculated. We will report within-trial cost-effectiveness; if the trial produces sufficient evidence to plausibly model future quality of life or costs (e.g. based on projected failure rates) we will also extrapolate long-term cost-effectiveness beyond the trial period.

An important component of this trial will be assessment of cost. Therefore, an accurate record of procedures at each of the proposed centres is essential. To evaluate costs of each type of surgery, information from the operating theatres will be collected. Theatre managers will be contacted and visited at each site. Resources used, equipment costs and standard procedures

for rotator cuff repairs will be looked at. Per case information will also be analysed. A checklist of equipment, consumables, implants, time and staff utilized during each case will be completed by theatre staff. Information from theatres will be collected by the Oxford UKUFF office and used in a cost comparison between the arthroscopic and open surgery.

6. SAMPLE SIZE AND FEASIBILITY

6.1 Sample size sought

Based on our experience of using and developing the OSS score in a variety of settings, a 3 point difference (0.33 of a SD) would be deemed a clinically important change. Using the informal survey of surgeons' preferences, we aim to recruit at least 8 surgeons to stratum A, 10 to stratum B and 40 to stratum C. From this we have assumed the following numbers of participants in each strata: Stratum A – 70 participants in each group; stratum B - 120 arthroscopic surgery : 120 Rest then Exercise management and stratum C - 120 open surgery : 120 Rest then Exercise management (see Table 1) giving 690 participants in total.

Table 1 – Proposed number of randomised participants

	Arthroscopic surgery	Open surgery	Rest then Exercise
Stratum A	70	70	70
Stratum B	120	None	120
Stratum C	None	120	120

For comparison (i), results from the arthroscopic surgery and Rest then Exercise groups in strata A and B can be combined without introducing any systematic bias (resulting in 190 arthroscopic:190 Rest then Exercise). Such a study has greater than 80% power at 2.5% significance level (to account for multiple testing) to detect a difference in mean OSS of 0.33 of a SD, using a two sample two-sided t-test. With an SD of about 9, this would translate to having adequate power to be able to detect a difference in mean OSS score between two groups of about 3 units.

For comparison (ii), the same power (>80%) and detectable difference (0.33 of a SD) as given above are obtained by combining the open surgery and Rest then Exercise management groups in strata A and C (n=190 in each arm).

[figure not shown]
For comparison (iii), due to the small numbers of surgeons willing to randomise to this comparison we propose to use a mixture of direct (randomised) and indirect (non randomised) comparisons. The direct comparison is in stratum A where 70 arthroscopic: 70 open surgeries have 80% power at 2.5% significance to detect a difference of 0.5 of a SD. An indirect comparison using only the results from strata B and C would have 80% power (at 2.5% significance level) to detect a difference of 0.55SD. Combining the direct and indirect comparison estimate (using recognised meta analysis techniques) gives approximately 80% power at 2.5% significance to detect a difference of 0.38SD.

Attrition is expected to be low (10%) as are the effects of clustering of outcomes within surgeon19,20 (intra cluster correlation less than 0.03). Whilst we do not have a direct estimate from a shoulder trial, other orthopaedic datasets available to our team (e.g. KAT) support this low ICC estimate. Both these factors require the sample size to be inflated; however, the primary analysis adjusts for baseline OSS score which conversely allows the sample size to be decreased by a factor of $(1 - \text{correlation squared})^{21}$. Our previous studies (section 3.2) showed that the correlation in the OSS score pre surgery to 6 months post surgery in patients similar to potential trial participants was 0.57. Assuming a conservative correlation of 0.5 implies that the sample size could be reduced by 25% and still maintains the same power. Therefore, a study with 690 participants will still have sufficient power to detect a clinically important change in each comparison assuming attrition and clustering accounts for approximately 25% of variation in the data.

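### The closing power statement covers all three comparisons, but the protocol's own figure for open versus arthroscopic surgery is 80% power at 0.38 SD, not at the clinically important 0.33 SD

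*Protocol*

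**What the plan says.** Section 5 lists three principal comparisons. The third, open versus arthroscopic surgery, draws on all three strata. Section 5.3 says that it will be estimated by meta-analysis of a direct estimate (stratum A) and an indirect one (strata B and C).

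Section 6.1 fixes the target: "a 3 point difference (0.33 of a SD) would be deemed a clinically important change". For comparison (i), with 190 per arm, it states "greater than 80% power at 2.5% significance level (to account for multiple testing" and a difference of 0.33 SD, "using a two sample two-sided t-test". Comparison (ii) is given the same power and difference.

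For comparison (iii) every stated detectable difference is larger than 0.33 SD:
- Direct evidence: "70 arthroscopic: 70 open surgeries have 80% power at 2.5% significance to detect a difference of 0.5 of a SD".
- Indirect evidence: 80% power at 0.55 SD.
- The two combined: the section says this "gives approximately 80% power at 2.5% significance to detect a difference of 0.38SD".

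The section then sets a 25% reduction from adjusting for baseline score (correlation 0.5) against about 25% lost to attrition and clustering. It concludes that "690 participants will still have sufficient power to detect a clinically important change in each comparison".

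**The concern.** Because comparison (iii) is a principal comparison, the closing sentence includes it. The clinically important difference is defined a few lines earlier as 0.33 SD, and the best figure given for (iii) is 0.38 SD at 80% power. Both statements cannot hold at 80% power unless something later in the section improves (iii). The only candidate is the baseline adjustment, and the closing sentence already spends that on attrition and clustering.

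At stake is how the trial is described to those who rely on section 6.1. A reader who takes the closing sentence at face value would credit the open versus arthroscopic comparison with the same ability to detect 3 points as the two comparisons with Rest then Exercise. It has less.

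**Working it through.** **Inputs, all from section 6.1 unless noted.** Important difference 3 points, or 0.33 SD. SD: "With an SD of about 9", so 3/9 = 0.333. Stratum A has 70 per arm; strata B and C have 120 per arm. Significance is 2.5%, which agrees with section 5.3 ("Statistical significance will be at the 2.5% level"). The two-sided test is stated for (i) and is taken to apply to (ii) and (iii). Normal approximation: z for two-sided 2.5% = 2.2414; adding z for 80% power (0.8416) gives 3.0830.

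**Formulae.** In SD units, with information I = 1/variance:
- power = Φ(d·√I − 2.2414)
- difference detectable with 80% power = 3.0830/√I

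**Information.**
- (i) and (ii): 190/2 = 95
- (iii) direct: 70/2 = 35
- (iii) indirect, four arms of 120: 1/(4/120) = 30
- (iii) combined: 35 + 30 = 65

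**Reproducing the protocol's figures.**

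| Comparison | Protocol states | Recomputed power at that difference | Difference at 80% power |
|---|---|---|---|
| (i), (ii) | >80% at 0.33 SD | Φ(0.33×9.747 − 2.2414) = 83.5% | not needed |
| (iii) combined | about 80% at 0.38 SD | Φ(0.38×8.062 − 2.2414) = 79.5% | 3.0830/8.062 = 0.382 SD |
| (iii) direct | 80% at 0.5 SD | Φ(0.5×5.916 − 2.2414) = 76.3% (exact t 75.5%) | 3.0830/5.916 = 0.521 SD |
| (iii) indirect | 80% at 0.55 SD | Φ(0.55×5.477 − 2.2414) = 78.0% | 3.0830/5.477 = 0.563 SD |

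The figures for (i), (ii) and combined (iii) reproduce. The direct and indirect figures miss slightly.

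**Comparison (iii) at the important difference.** On the section's premise that gain and loss cancel, the information is 65 × 0.75/0.75 = 65.
- At 0.33 SD: Φ(0.33×8.062 − 2.2414) = Φ(0.419) = 66.2%
- At 3/9 SD: Φ(0.3333×8.062 − 2.2414) = Φ(0.446) = 67.2%
- Detectable difference in points: 0.382 × 9 = 3.4

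**How far this depends on the cancellation** (power for (iii) at 0.33 SD):
- Correlation 0.5, 10% attrition, no clustering: I = 65×0.9/0.75 = 78; power 75.0% (75.9% at 3/9).
- Correlation 0.5, no attrition, no clustering: I = 65/0.75 = 86.7; power 79.7% (80.6% at 3/9).
- Correlation 0.5, 10% attrition, intra-cluster correlation 0.03, with a simple per-surgeon design effect for 8, 10 and 40 surgeons: 54.8%. The design-effect form is an assumption made for this check and is not in the protocol.

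**Sidedness.** A one-sided 2.5% test would give 75.8% at 0.33 SD. It would also give 86.5% at 0.38 SD, which does not match the stated 80%. The two-sided reading is the one that reproduces the protocol.

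**The case against.** The strongest reply is that the shortfall is small and in plain view. The 0.38 SD is printed, and section 6.1 explains it by the few surgeons willing to randomise between the two operations. The gap is 3.4 against 3 points on an SD given only as about 9. That stands: nothing is concealed, and the correct combined figure is already there. It does not remove the contradiction, because the closing sentence still names each comparison.

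A second reply is that 66% is conditional. It holds only if baseline adjustment exactly offsets attrition and clustering. Patients are randomised within surgeons' strata and minimised by centre, so clustering might cost less than allowed for. With the observed correlation of 0.57, 10% attrition and no clustering, power for (iii) would be 79.7% at 0.33 SD (80.6% at 3/9). This stands as a reason to give the figure with its assumption. It does not rescue the sentence: section 6.1 itself says that attrition and clustering require inflation, it chooses 0.5 over 0.57, and the 0.57 runs only to 6 months while the primary outcome is at 24 months.

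A third reply is that the direct and indirect figures are rounding. This is probably right. Pooling the printed 0.5 and 0.55 SD would give 1/√(1/0.5² + 1/0.55²) = 0.37 SD, whereas the printed 0.38 matches the unrounded 0.382. The error does not carry forward.

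A reader might also infer that a non-significant (iii) is bound to be misread as showing no difference. The protocol does not say so, and section 5.3 already provides for confidence intervals.

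**Conclusion.** The point holds. The claim of sufficient power for the clinically important change in each comparison is not supported for comparison (iii). By the protocol's own figures, (iii) has about 80% power at 0.38 SD (3.4 points at SD 9). At 0.33 SD it has about 66%, or 67% at 3/9 SD. These figures assume a two-sided 2.5% test, the planned stratum sizes, and the stated offset of a 25% gain against about 25% lost. With a correlation of 0.5, 10% attrition and no clustering, power is about 75%.

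Stronger conclusions might be inferred, but the documents do not support them:
- That (iii) has 66% power without qualification. This is the value on the section's own premise, and it moves with clustering and the baseline correlation.
- That the whole sample size calculation is wrong. The figures for (i), (ii) and combined (iii) all reproduce.
- That the direct and indirect figures undermine the combined one. They are small misses and do not affect it.

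**What to change.** In section 6.1:
- Limit the closing sentence to comparisons (i) and (ii).
- Add that, on the same assumption that baseline adjustment offsets attrition and clustering, comparison (iii) has about 80% power for 0.38 SD (3.4 points) and about 66% for 0.33 SD. A non-significant (iii) is therefore to be interpreted by its confidence interval against 3 points.
- Change the intermediate figures to 80% power at 0.52 SD (direct) and 0.56 SD (indirect). The combined 0.38 SD stays as it is.

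The cost is a few restated sentences. The sample size, significance level and analysis do not change.
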